prospective, randomized, double-blind placebo controlled study. The study is designed to evaluate the efficacy, safety, and tolerability of transdermal patch of Rotigotine (RTG) versus placebo (PLC) as add-on therapy with AChEI in patients with mild AD according to the consensus diagnostic criteria and MMSE score of ≥18 and ≤24 at screening. Two groups of patients with mild AD will be involved (50 patients each). One group will be assigned to treatment with RTG 4 mg and the other one to PLC as add on to AChEI therapy. Clinical and neurophysiological measurements will be collected before and after drug administration.

120 SECTION 3. ABBREVIATIONS AND DEFINITIONS

- 121 **A** β : amyloid- β peptides
- 122 **AChEI:** acetylcholinesterase inhibitor
- 123 **AD:** Alzheimer's disease
- 124 ADAS-Cog: Alzheimer's Disease Assessment Scale—Cognitive subscale
- 125 ADCS-ADL: Alzheimer's Disease Cooperative Study–Activities of Daily Living Inventory
- **ADDF:** Alzheimer's Drug Discovery Foundation
- 127 AE: adverse event: Any untoward medical occurrence in a patient or clinical investigation subject
- administered a pharmaceutical product that does not necessarily have a causal relationship with this
- treatment. An adverse event can therefore be any unfavorable and unintended sign (including an abnormal
- laboratory finding), symptom, or disease temporally associated with the use of a medicinal (investigational)
- product, whether or not related to the medicinal (investigational) product.
- 132 **ANOVA:** analysis of variance
- 133 **APOE:** apolipoprotein E
- 134 Blinding: A procedure in which one or more parties to the trial are kept unaware of the treatment
- assignment(s). Blinding will remain in effect until final database lock. A double-blind study is one in which
- neither the patient nor any of the investigator who are involved in the treatment or clinical evaluation of the
- subjects are aware of the treatment received.
- 138 **CDR:** Clinical Dementia Rating Scale
- 139 CRF: Case report form, a printed or electronic form for recording study patients' data during a clinical
- study, as required by the protocol.
- 141 **CSF:** cerebrospinal fluid
- 142 DA: dopamine
- 143 **EEG:** electroencephalogram
- 144 Efficacy: Efficacy is the ability of a treatment to achieve a beneficial intended result under controlled
- 145 conditions.
- End of study (trial): The date of the last visit or last scheduled procedure shown in the Study. Schedule for

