
216

217

218

219

220

221

222

223

224

225

226

227

228

229

230

231

232

233

234

235

236

237

238

239

240

(TMS) during electroencephalography (EEG) will allow us to understand how dopamine agonists are able to modulate the cortical activity of the prefrontal cortex in AD patients (Kähkönen et al., 2005; Julkunen et al., 2008), likely trough DA terminals originating from the ventral tegmental nucleus, defining the neurophysiological biomarkers of clinical improvement.

SECTION 5: OBJECTIVES

The study is designed to evaluate the efficacy, safety, and tolerability of transdermal patch of Rotigotine (RTG) 4mg versus placebo (PLC) as add-on therapy with AChEI in patients with mild AD according to the consensus diagnostic criteria and MMSE score of ≥18 and ≤26 at screening. Additionally, the study aimed to test if RTG induced change in brain physiology. To this aim, we used a multimodal neurophysiological tool, such as transcranial magnetic stimulation combined with electroencephalography (TMS/EEG), to measure changes in cortical activity in the prefrontal cortex. We expected that Rotigotine could represent a valid treatment for cognitive dysfunction in AD patients, slowing the cognitive and functional decline and increasing cortical activity of the prefrontal cortex.

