6.1. Summary of Study Design

This is a 24-week, randomized, double-blind, placebo-controlled, Phase 2 study, comparing Rotigotine (Neupro, UCB pharma) with placebo for 24 weeks in approximately 100 patients with mild AD, defined as having a Visit 1 MMSE score of 18 to 26. Patients will be adaptively randomized (Lin et al. 2016) in a 1:1 ratio stratified by sex, age, APOE genotype, education and screening severity (MMSE) to one of the following treatment groups: Placebo group; RTG 4mg group. All patients started the treatment with a package containing 7 patches of RTG 2mg/placebo, and continued treatment with 6 packages, each one containing 30 patches of RTG 4mg/placebo depending on the arm of randomization. The primary hypothesis being tested is that Rotigotine will slow the cognitive and functional decline of AD as compared with placebo in patients with mild AD.

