2. STATISTICAL ANALYSIS PLAN

2.1. Determination of Sample Size

A total of 94 randomly assigned patients (47 per group) were planned on the basis of our previous study in which we assessed the effects of rotigotine on cortical plasticity and cognitive functions in a small sample of Alzheimer's disease patients (Koch et al., 2014). In that pilot study, a significant (although unpowered) difference was observed in pre-post (12 weeks) treatment with rotigotine in n=7 patients in both the cognitive measures MMSE (mean pre=21.73, SD=4.14; mean post=23.23, SD=3.93) and in FAB (mean pre=10.85, SD=4.43; mean post=12.32, SD=4.48). Treatment duration of the present study is twice larger than the one of the pilot study thus a larger effect size is expected. However, for precautionary reasons, we consider the same effect sizes found in the previous work (equal to 0.48 for MMSE and equal to 0.42 for FAB computed as post-pre means over standard deviation of difference post-pre), for the sample size calculation of the present study. In detail, adopting a two-tailed paired t-test, with type I error alpha=0.05 and a plausible correlation between pre-post measured variables of 0.7, the FAB effect size equal to 0.42 requires a minimum sample of n=46 for reaching a power of 0.8. For MMSE, this sample size allows to reach a power of 0.9. The minimum total sample size was then augmented up to N=92 considering the matched placebo group.

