2.3 Statistical and Analytical Plans

2.3.1. General Considerations

Unless otherwise noted, all tests of treatment effects will be conducted at a 2-sided alpha level of 0.05; 2-sided confidence intervals will be displayed with a 95% confidence level. All tests of interactions between treatment and other factors will be conducted at an alpha level of 0.05. All analyses will follow the intent-to-treat (ITT) principle unless otherwise specified. An ITT analysis is an analysis of data by the groups to which subjects are assigned by random allocation, even if the subject does not take the assigned treatment, does not receive the correct treatment, or otherwise does not follow the protocol.

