by means of Shapiro-Wilks' test. The sphericity of the data will be tested with Mauchly's test; when sphericity is violated (i.e. Mauchly's test < 0.05) the Greenhouse–Geisser correction will be used. Pairwise comparisons will be corrected by the Bonferroni method. Safety analyses for the treatment period will include comparisons between rotigotine and placebo groups by 2-sided 0.05 significance level Chi-square tests. Statistical analyses will be performed with IBM SPSS statistics, version 24.0 and R software; significance alpha level test is set up at 0.05.

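### Safety is a stated aim, but the SAP names only a 0.05 chi-square test for comparing the arms and no effect measure; for uncommon adverse events a non-significant result would say little about tolerability

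*Combined protocol and SAP*

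**What the plan says.** Section 5 (Objectives) states: "The study is designed to evaluate the efficacy, safety, and tolerability of transdermal patch of Rotigotine (RTG) 4mg versus placebo". The synopsis gives the same aim. The primary and secondary objectives in 5.1 and 5.2 contain no safety hypothesis.

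The between-arm safety analysis is one sentence near the end of SAP 2.3.4, a section headed for efficacy outcomes. It says that safety analyses will include "comparisons between rotigotine and placebo groups by 2-sided 0.05 significance level Chi-square tests". It does not name event categories, an effect measure, or how the result will be interpreted, and it does not say whether a continuity correction applies.

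SAP 2.3.1 adds a general rule: "2-sided confidence intervals will be displayed with a 95% confidence level". It does not mention safety.

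The sample size in SAP 2.1 comes from efficacy alone: "the FAB effect size equal to 0.42 requires a minimum sample of n=46 for reaching a power of 0.8". The planned number is given there as follows: "A total of 94 randomly assigned patients (47 per group) were planned". The synopsis gives 50 per arm. Neither place states power or precision for any safety measure, and the documents give no expected adverse-event rate for either arm.

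**The concern.** A significance test answers whether the data are surprising if the two risks are equal. It does not say how large an excess risk the data leave open, and that is what a tolerability conclusion needs. In a trial sized for a cognitive change, the test can easily be non-significant for an event that is truly two or three times as frequent on rotigotine.

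The SAP gives the authors a p-value and no other specified summary of the between-arm safety difference. The protocol also starts from earlier work in which the patch was reported as well tolerated, so a null chi-square result could readily be presented as confirmation. The statement at stake is whether rotigotine is safe and well tolerated as an add-on in mild Alzheimer's disease.

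**Working it through.** **1. The plan's own figure.** SAP 2.1 uses a two-tailed paired t-test, effect size 0.42, alpha 0.05. The noncentrality at n = 46 is 0.42 × √46 = 2.85, and the exact power is 0.796; n = 47 gives 0.805. The stated power of 0.8 at n = 46 is reproduced to rounding. It concerns change within one group and carries no information about safety.

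**2. Power of the planned safety test.** Inputs: 47 per arm (SAP 2.1) and two-sided alpha 0.05 (SAP 2.3.4). The event rates are assumptions. With x events on rotigotine and y on placebo,

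X² = 94 × [x(47 − y) − y(47 − x)]² / [47 × 47 × (x + y) × (94 − x − y)].

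Power is the sum, over all pairs (x, y) with X² > 3.84, of Bin(x; 47, p_R) × Bin(y; 47, p_P). For Yates, 47 is subtracted from the absolute value of the bracket (not below zero) before squaring.

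| Placebo → rotigotine | Ratio | Pearson | Yates |
|---|---|---|---|
| 5% → 10% | 2 | 0.17 | 0.06 |
| 10% → 20% | 2 | 0.29 | 0.18 |
| 15% → 30% | 2 | 0.42 | 0.32 |
| 20% → 40% | 2 | 0.57 | 0.48 |
| 25% → 50% | 2 | 0.71 | 0.63 |
| 5% → 15% | 3 | 0.40 | 0.22 |
| 10% → 30% | 3 | 0.71 | 0.60 |
| 15% → 45% | 3 | 0.91 | 0.86 |

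With 50 per arm, Pearson power is 0.30 for 10% → 20% and 0.73 for 10% → 30%, so the choice between 47 and 50 hardly matters.

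**3. Where detection becomes more likely than not.** Raising the placebo rate in steps of 0.5 points, power first reaches 0.5 at these rates:
- doubling: 18% (Pearson), 21% (Yates);
- tripling: 7% (Pearson), 9% (Yates).

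**4. What a non-significant table can hide.** Take 8/47 on rotigotine and 3/47 on placebo.
- X² = 94 × (8 × 44 − 3 × 39)² / (47 × 47 × 11 × 83) = 94 × 235² / 2,016,817 = 2.57, so p = 0.11.
- Risk difference = 0.1702 − 0.0638 = 0.1064.
- Wilson 95% limits: 0.0889 to 0.3014 (rotigotine) and 0.0219 to 0.1716 (placebo).
- Newcombe lower limit = 0.1064 − √[(0.1702 − 0.0889)² + (0.1716 − 0.0638)²] = −0.029.
- Newcombe upper limit = 0.1064 + √[(0.3014 − 0.1702)² + (0.0638 − 0.0219)²] = 0.244.

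The result is 10.6 points, 95% CI −2.9 to 24.4. The p-value alone does not show that an excess of up to 24 points is still compatible with the data.

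**5. Is the chi-square itself at fault?** With 5% in both arms, the uncorrected Pearson test rejects with probability 0.051, so its type I error is acceptable there. Fisher's exact test has power 0.18 for 10% → 20%, against 0.29 for Pearson.

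**The case against.** The best defence has four parts.

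- **The test is not the whole of safety.** SAP 2.3.4 uses inclusive wording (analyses will include the test), and 2.3.1 promises 95% intervals in general. Section 9.4 has adverse events, vital signs and examinations recorded at each visit, with an independent Data Monitoring Committee. This stands. A reader might infer that safety is judged by the chi-square test alone, and the documents do not support that. But the committee watches patients during the trial and does not define the final comparison. The interval rule also needs a named quantity, and none is given for safety.
- **Large excesses are often detected.** A reader might infer that any doubled or tripled rate would usually be missed. The table above shows otherwise: 0.57 for 20% → 40%, 0.71 for 10% → 30% and 0.91 for 15% → 45% with Pearson. The claim holds only at low placebo rates.
- **No rule equates p > 0.05 with safety.** Correct. The documents contain no such rule, so the risk is one of later interpretation that the SAP leaves open. Nor does every null table leave a 20-point excess open: the Newcombe upper limit is 15.1 points for 5/47 vs 4/47 and 10.5 for 2/47 vs 2/47.
- **Low power for harms is normal in a phase IIa trial.** Agreed. That argues for estimation, not for more patients.

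A further step, requiring an exact test, is also not supported. Step 5 shows that Fisher's test would be less sensitive to harm, and that Pearson's type I error is not a clear problem at these counts.

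**Conclusion.** The concern holds in a limited form. For uncommon events, a non-significant chi-square result at this sample size is weak evidence of tolerability, and the SAP specifies no safety effect measure that would show the uncertainty. The limits of about 18–21% (doubling) and 7–9% (tripling) rest on assumed event rates, 47 analysed patients per arm, and detection meaning p < 0.05 two-sided; the range in each covers the test without and with Yates correction. SAP 2.1 makes no allowance for dropout, and fewer analysed patients would generally lower the power. Specific adverse events, serious events and discontinuations could plausibly fall below these limits, but the documents give no rates to confirm it. This is a cheap improvement to the reporting plan and not a flaw in the design.

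**What to change.** Amend the safety sentence in SAP 2.3.4 as follows.

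- For any adverse event, serious adverse event, adverse event leading to discontinuation, and each adverse-event category, report the number and percentage of patients per arm.
- For each, give the risk difference (rotigotine minus placebo) with a 95% Newcombe score interval.
- Label any chi-square p-value as descriptive.
- Add a sentence such as: A non-significant difference will not be interpreted as evidence of safety; the safety and tolerability conclusion will be worded from the 95% interval for the risk difference.

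The cost is a few lines of SAP text and one more column in the adverse-event tables, with no extra patients or data. The small downside is a less favourable safety statement, because it must say which excess risks are not ruled out.
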